1. SYNOPSIS

This is a brief summary. For details refer to the body of the protocol.

Protocol Number:

Protocol Title: **Physiologic interindividual variability of volume and atrophy in central nervous system structures with focus on spinal cord as measured by quantitative magnetic resonance imaging.**

Version Number: <1>

Study Indication: Healthy controls

Rationale for the Study: Spinal cord (SC) involvement is prevalent in multiple sclerosis (MS) and contributes importantly to disease progression. To be able reliably evaluate spinal cord volume and its changes in MS patients we need to understand variability of these parameters in sex and age matched healthy controls (HC). To date, no generally available data about these parameters in HC are available.

The objective of this study is to investigate age and sex matched HC by MRI to get the basic set of the data representing both cross sectional values and its longitudinal changes.

The present study will also investigate different strategies how to normalize the absolute spinal cord and brain volume data, what is a relationship between spinal cord volume and brain volume and what is the best protocol to be used in a routine clinical practice.

Study Objectives and

Objectives

Endpoints:**Primary objective**

To examine 102 healthy controls on MRI to get data about spinal cord volume. This data will be used to compare spinal cord volume in HC with spinal cord volume of age and sex matched multiple sclerosis patients.

Secondary Objectives

- Test several normalization strategies and choose the best variable or set of variables to normalize spinal cord volume
- Determine inter-subject variability in spinal cord volume in healthy controls
- Determine inter-subject variability in different whole and regional brain volumes in healthy controls

Tertiary objectives

- Determine relationship between spinal cord volume and whole and different regional brain volumes in healthy controls.
- Optimize MRI protocol (different sequences) for separation of white and gray matter in cervical spinal cord.

Endpoints**Primary Endpoint**

Establishing pathological cut-offs for spinal cord volumes. By using those we will be able to discriminate with the highest sensitivity and specificity HC from MS patients. The analysis will be done both cross-sectionally and longitudinally.

Secondary Endpoints

- Description of results of different normalisation strategies, using different variables, e.g. sex, age, body height, height of C3 vertebra (or other vertebra

derived metrics), total intracranial volume (TIV).

- Description of absolute and normalised spinal cord volume and its variability in predefined spinal segments in different age and sex groups of HC.
- Description of absolute and normalised brain volumes in HC measuring whole brain, TIV and different regional brain volumes, especially – gray and white matter compartment, corpus callosum, thalamus, and cerebellum.

Tertiary Endpoints

- Correlation between spinal cord volume (total and GM, WM separately) and several brain metrics (total brain volume, GM, WM, lateral ventricles, thalamus, corpus callosum, brainstem and cerebellum) in HC.
- Comparison of results from different MRI protocols

Study Design:	Prospective, longitudinal, monocentric, interventional study
Study Location:	Czech Republic
Number of Planned Subjects:	102 subjects – intended as healthy controls (HC) from general population
Study Population:	This study is conducted in healthy subjects. Detailed criteria are described in the protocol.
Statistical Methods:	Binary or categorical variables will be presented as frequency distributions. Continuous variables will be reported by summary statistics: mean and standard deviation (SD) or median and range. The relationship between age and spinal cord volume will be determined separately for female and male patients in different decades to determine sex- and age-related effects on spinal cord volume. The spinal cord volume (and eventually also spinal cord gray- and white matter volumes) will be compared in three age-specific groups: 18-30 years, 30-40 years and 40-60

CONFIDENTIAL

years.

Annualised change of spinal cord volume will be calculated for each participant as the slope of a regression line fitted to all four timepoints (M0, 12, 24 and 36) with the assumption of linear change over time for each participant and for all participant (in a decade-specific manner) together.

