6.2.2. General Methods of Analysis

In general, continuous variables will be presented with summary statistics (mean, SD, median, range) and a 95% confidence interval (CI), and categorical variables will be presented with frequency distributions.

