6.3.2. Sample Size Calculation

The exact sample size calculation is difficult due to several problems – there is very limited data about spinal cord volume in both MS patients and HC. In addition to that spinal cord volume is scanner and protocol specific, so it is not possible to use directly data from other centres.

Based on current knowledge we can estimate that MS patients are losing spinal cord volume 3-5 times faster compare to HC. The problem is that this can be age and sex specific and different in different MS phenotypes. So, it is reasonable to choose the group of HC that the best copy a typical MS patient population, i.e. ratio of male : female 1:2 and age range 18-60 years.

From the statistical point of view is generally recommended to have at least 10 subjects in each age and sex specific subgroup (see Table 1). Taking into account that the study is planned for 4 years and there is a risk of drop out of some participants we recommend to increase number of participants in each group by 2.

Based on this conditions we recommend to enrol:

Table 1.

Age range / Sex	Male	Female
18-30 years	12	22
30-40 years	12	22
40-60 years	12	22
Total	36	66

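### The synopsis aims to establish how sex and age affect cord volume by analysing women and men separately, but specifies no male-female contrast and no sex-by-age estimate

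*Combined protocol and SAP*

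**What the plan says.** The Statistical Methods entry of the synopsis states that the age-volume relationship "will be determined separately for female and male patients in different decades to determine sex- and age-related effects on spinal cord volume". The next sentence says that cord volume "will be compared in three age-specific groups: 18-30 years, 30-40 years and 40-60" years; it names no test and does not mention sex. The synopsis also plans annualised change per participant and for all participants together by decade.

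Section 6 does not develop the analysis by sex:
- 6.2.3 covers logistic regression and ROC analysis of healthy controls against MS patients.
- 6.2.4 gives summaries and confidence intervals, and the tests it names compare patients with controls.
- 6.2.5 covers cord-brain correlations and MRI protocols.
- Sex and age are candidate normalisation variables (synopsis, 2.3.2, 6.1.2), but only the results are to be described and no model is stated.

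Section 6.3.2 fixes the numbers: "ratio of male : female 1:2 and age range 18-60 years", with "at least 10 subjects in each age and sex specific subgroup". Table 1 plans 36 men and 66 women.

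**The concern.** The aim includes a sex effect, while the stated method is two within-sex analyses. Two such analyses set side by side do not yet compare the sexes, and the plan does not say how they are to be compared. The usual shortcut is to note that the age effect is significant in one sex and not in the other, and to report a sex difference. That inference is unsound, because the difference between a significant and a non-significant result need not itself be significant.

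The study is meant to supply sex- and age-matched healthy values against which MS patients are judged (2.1, 2.2.1). A reported age effect in women only, or in men only, would bear on how those values are understood and used.

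**Working it through.** **Inputs from the documents.** Section 6.3.2 gives a minimum of 10 per cell, a 1:2 male-to-female ratio (hence 20 women per age group) and the advice to "increase number of participants in each group by 2". This reproduces Table 1: men 3 × (10 + 2) = 36, women 3 × (20 + 2) = 66, total 102. If the whole dropout allowance is used, 30 men and 60 women remain. I read the synopsis's reference to patients as meaning the enrolled healthy controls.

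**Assumptions.** No age effect, SD, significance level or power is given for this question; 6.3.2 says "The exact sample size calculation is difficult due to several problems" and that "there is very limited data about spinal cord volume in both MS patients and HC". I therefore assume the same true age-volume correlation r in both sexes, over a range, and a two-sided 5% test, in line with the 95% intervals of 6.2.2.

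**Power within one sex (Fisher z).** Power ≈ Φ(atanh(r)·√(n − 3) − 1.96), plus a negligible or small opposite tail. At r = 0.3, atanh(r) = 0.3095.
- Women: 0.3095 × √63 = 2.457; Φ(0.497) = 0.690.
- Men: 0.3095 × √33 = 1.778; Φ(−0.182) = 0.428.

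**Chance of significance in exactly one sex.** P = Pw(1 − Pm) + Pm(1 − Pw). At r = 0.3: 0.690 × 0.572 + 0.428 × 0.310 = 0.527.

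| r in both sexes | Power, 66 women | Power, 36 men | Women only | Men only | Exactly one |
|---|---|---|---|---|---|
| 0.1 | 13% | 9% | 11% | 8% | 19% |
| 0.2 | 36% | 21% | 29% | 14% | 42% |
| 0.3 | 69% | 43% | 39% | 13% | 53% |
| 0.4 | 92% | 68% | 29% | 5% | 35% |
| 0.5 | 99% | 88% | 12% | 1% | 12% |

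(Entries are rounded separately, so sums can differ by a point.)

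**Sensitivity.**
- With 60 women and 30 men, exactly-one results are about 40%, 54% and 43% at r = 0.2, 0.3 and 0.4.
- Simulated within-sex regressions (20,000 runs per setting, 66/36) give 42%, 53% and 32%.
- With three age groups instead of a continuous age (22 women or 12 men per group), a common effect of Cohen's f = 0.25 gives 45%, and f = 0.4 gives 48%.

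**Role of the unequal split.** With 51 in each sex, exactly-one results are 41%, 49% and 28% at r = 0.2, 0.3 and 0.4. The imbalance thus adds about 1, 4 and 7 points. Its main effect is on direction: at r = 0.3 equal groups divide the 49% evenly between the sexes, while 66/36 gives about 3 to 1 (39% against 13%).

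**What a joint model gives.** In the same simulations at 66/36, the sex-by-age test rejected in 4.8% to 5.2% of runs when the slopes were equal. A sex difference in mean volume of 0.58 SD has 80% power at 66/36.

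**Power of the interaction.** Taking a slope difference as a difference in correlations (similar age spread and residual SD in both sexes), SE = √(1/63 + 1/33) = 0.215.
- r = 0 against 0.3: 0.3095/0.215 = 1.44; Φ(1.44 − 1.96) ≈ 0.30.
- r = 0 against 0.4: 0.4236/0.215 = 1.97; power about 50%.
- 80% power needs a Fisher-z difference of 2.80 × 0.215 ≈ 0.60.

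**The case against.** The strongest reply is that this is a gap in specification and not a faulty analysis. Separate fits give independent means and slopes by sex, and their differences and intervals follow directly; the point estimates equal those of a model with a full sex-by-age interaction. This stands. A reader might infer that the plan cannot test a sex effect at all, but the documents support only that no contrast is specified.

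Second, no section says that effects will be judged by within-sex p-values. The matching secondary endpoint is descriptive, and 6.2.4 bases population inference on confidence intervals. This also stands: the percentages are conditional on that way of reading the results. The plan states no other rule for reaching a conclusion about sex, so the risk is open.

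Third, a reader might infer that the plan gives up power for an age effect common to both sexes. All 102 would give 87% power at r = 0.3, against 69% and 43% separately. But the synopsis also plans a comparison of three age groups with no split by sex stated, and annualised change for all participants together. The sex-specific analysis is therefore not shown to be the only age analysis.

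Fourth, sex and age are candidate normalisation variables, so their influence on cord volume will be looked at. No model is given for that work, so it does not supply the missing contrast.

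**Conclusion.** The point holds as a gap in the analysis plan: an effect of sex is to be determined and no estimate of it is defined. Under an identical modest age effect (assumed r = 0.2 to 0.4) and judgement by within-sex significance, 35% to 53% of studies would show the effect in one sex only. Outside that range the risk is smaller.

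Two further readings go beyond the documents. One is that the false pattern arises because 66 and 36 differ; equal groups would produce most of it, and the split chiefly decides which sex it favours. The other is that such a finding would pass into the primary cut-offs; section 6.2.3 derives those from logistic regression and ROC analysis and does not mention this step. The issue should be corrected, but it does not undermine the primary analysis.

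**What to change.** Replace the sentence in the synopsis, and add a matching paragraph to section 6.2.4, along these lines:
- Fit one model for spinal cord volume in all participants with age, sex and a sex-by-age term, and name the visit to which it applies.
- Report the sex difference (at a stated age), the age slope in each sex and the difference between slopes, each with a 95% confidence interval.
- Base any claim of a sex-specific age effect on the slope difference and its interval, not on two within-sex p-values.
- Keep the tables by sex and age group as description.
- State that a non-significant interaction will not be read as equal slopes, and will not trigger a switch to a common slope. With about 30% power for r = 0 against 0.3, such a rule would usually pool away a real difference.

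The change needs no extra participants, visits or scans; it costs only wording in the analysis plan.

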2.3.2. Secondary Endpoints

- Description of results of different normalisation strategies, using different variables, e.g. sex, age, body height of HC, height of C3 vertebra (or other vertebra derivate metrics).
- Description of absolute and normalised spinal cord volume and its variability in predefined spinal segments in different age and sex groups of HC.
- Description of absolute and normalised brain volumes in HC measuring whole brain (total intracranial volume TIV) and different regional brain volumes, especially – gray and white matter compartment, corpus callosum, thalamus, and cerebellum.

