6.1.2. Secondary Endpoints

- Description of results of different normalisation strategies, using different variables, e.g. sex, age, body height of HC, height of C3 vertebra (or others vertebra derivate metrics).
- Description of absolute and normalised spinal cord volume and its variability in predefined spinal segments in different age and sex groups of HC.
- Description of absolute and normalised brain volumes in HC measuring whole brain (total intracranial volume TIV) and different regional brain volumes, especially – gray and white matter compartment, corpus callosum, thalamus, and cerebellum.

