6.2.4. Secondary Endpoints Analysis

For all secondary endpoints, continuous variables will be presented with summary statistics (mean, SD, median, range), and categorical variables will be presented with frequency distributions. The inference of population characteristics will be estimated by confidence intervals. The statistical testing (parametric/non-parametric tests) will be done to compare characteristics of central tendency and variability between patient's and HC's cohorts.

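### The one concretely specified age comparison of healthy-control cord volume uses three overlapping bands; a prespecified regression on continuous age would use the same data better

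*Combined protocol and SAP*

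**What the plan says.** The Synopsis (Statistical Methods) makes three statements about age:

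- "The relationship between age and spinal cord volume will be determined separately for female and male patients in different decades". I take the word patients there to mean the study's participants.
- Cord volume "will be compared in three age-specific groups: 18-30 years, 30-40 years and 40-60" years.
- Annualised change is estimated per person and "for all participant (in a decade-specific manner) together".

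The Synopsis defers to the main text ("For details refer to the body of the protocol"). There, Sections 2.3.2 and 6.1.2 list age among the candidate normalisation variables ("using different variables, e.g. sex, age, body height of HC") without saying whether it enters as continuous or grouped. Section 6.1.2 also has the secondary endpoint "Description of absolute and normalised spinal cord volume and its variability in predefined spinal segments in different age and sex groups of HC". Section 6.2.4 covers all secondary endpoints with summary statistics and confidence intervals; its statistical tests "will be done to compare characteristics of central tendency and variability between" the patient and control cohorts. Section 6.2.3 (primary endpoint) names no age term. The regressions in Section 6.2.5 relate cord volume to brain measures, not to age.

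Table 1 in Section 6.3.2 uses the same three bands as enrolment cells, on the principle of "at least 10 subjects in each age and sex specific subgroup".

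**The concern.** Sections 1 and 2.1 justify the study by the need to know what cord volume is normal for a given age and sex. The plan gives no model from which an expected volume at a given age could be read. The one concrete method, three bands, treats everyone aged 40 to 60 as having the same expected value.

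The bands are also not a partition. A 30-year-old or a 40-year-old belongs to two of them, in the Synopsis and in Table 1, and no rule assigns them. Decades are undefined, and the 40-60 band spans two. No passage says whether the band is fixed at entry, although each person is followed for three years. Two analysts could form different groups from the same data.

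At stake are the precision and reproducibility of a secondary, descriptive result.

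**Working it through.** **The plan's own figure.** Men: 3 × (10 + 2) = 36. Women, at the stated 1:2 ratio before the allowance: 3 × (20 + 2) = 66. Total 102, as stated.

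**Band overlap.** In completed years the bands hold 13 + 11 + 21 = 45 ages, while 18 to 60 holds 43; ages 30 and 40 are counted twice. With 34 people per band spread evenly, membership is unclear for 34/10 + 34/21 = 5.0 people (if recruitment in fact used exclusive bands) to 34/13 + 34/11 + 34/11 + 34/21 = 10.4 (if both bands recruit the shared ages).

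**Assumptions for the rest.** The documents give no SD, effect size, alpha or power. I assume 34 per band (12 men + 22 women, Table 1), uniform ages within bands, two-sided alpha 0.05, and an age-volume correlation r of 0.20 to 0.35.

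**Age variance kept by the bands.** Band midpoints 24, 35 and 50 have mean 36.33 and between-band variance 113.56. Within-band variance is (12² + 10² + 20²)/12/3 = 17.89. Total 131.44 (SD 11.46). Share kept: 113.56/131.44 = 0.864. Of the part lost, 33.33/53.67 = 62% lies inside the 40-60 band.

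**Power if age acts linearly.** Noncentral F with λ = N·R²/(1 − R²). R² = r² for a linear term (1 df) and for a three-knot spline (2 df); R² = 0.864·r² for bands (2 df). Example, r = 0.30, N = 102: linear λ = 102 × 0.09/0.91 = 10.09; bands λ = 102 × 0.0778/0.9222 = 8.60.

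| r (N = 102) | Linear | Spline | Bands | Loss v linear | Loss v spline |
|---|---|---|---|---|---|
| 0.20 | 0.533 | 0.427 | 0.373 | 16 points | 5 points |
| 0.25 | 0.733 | 0.628 | 0.557 | 18 points | 7 points |
| 0.30 | 0.882 | 0.806 | 0.737 | 14 points | 7 points |
| 0.35 | 0.962 | 0.925 | 0.875 | 9 points | 5 points |

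By sex at r = 0.30 (linear, spline, bands): 66 women 0.71, 0.60, 0.53; 36 men 0.45, 0.35, 0.30.

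**Power under other shapes.** Simulation, 6,000 runs, N = 102, r = 0.30, sex in the model:

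| True shape | Linear | Spline | Bands |
|---|---|---|---|
| Flat to 40, then falling | 0.75 | 0.78 | 0.60 |
| Peak at 40 | 0.12 | 0.78 | 0.50 |
| Step at 40 | 0.75 | 0.68 | 0.81 |

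**Precision of an expected value** (95% half-width in residual SD). Cell mean: 1.96/√12 = 0.57 for men, 1.96/√22 = 0.42 for women. Linear model: 1.96·√(1/n + (age − 36.33)²/SS), with SS = 36 × 131.44 = 4732 for men and 66 × 131.44 = 8675 for women. Spline: the same calculation with knots at the 10th, 50th and 90th percentiles of age.

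| Age | Men: cell | Men: linear | Men: spline | Women: cell | Women: linear | Women: spline |
|---|---|---|---|---|---|---|
| 18 | 0.57 | 0.62 | 0.89 | 0.42 | 0.46 | 0.66 |
| 24 | 0.57 | 0.48 | 0.52 | 0.42 | 0.35 | 0.39 |
| 35 | 0.57 | 0.33 | 0.48 | 0.42 | 0.24 | 0.36 |
| 50 | 0.57 | 0.51 | 0.51 | 0.42 | 0.38 | 0.38 |
| 60 | 0.57 | 0.75 | 1.02 | 0.42 | 0.55 | 0.75 |

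**Error of a single 40-60 mean.** At 40 or 60 it is ten years from the band centre: 10 × (r/11.46)/√(1 − r²) = 0.18 SD at r = 0.20 and 0.33 SD at r = 0.35.

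**The case against.** The strongest reply is that the endpoint asks for groups. It is a description by age and sex group, Table 1 recruits to those groups, and Section 6.2.4 gives summaries and confidence intervals for every secondary endpoint. No age hypothesis is sized, so power at an assumed correlation measures a test that the plan did not promise. Much of this stands. A reader might infer that the plan has no analysis of cord volume by age; that is not so, because the descriptive group analysis is there. What is missing is a stated model for the age relationship that the Synopsis separately announces.

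A second reply is that bands are not always worse. This stands too. It would be wrong to say that they win only when the true effect is a step: against a linear term they also do much better for a peak at 40 (0.50 against 0.12). Nor is the precision gain free. Most of it comes from assuming linearity. A spline by sex spends three parameters per sex, as three band means do, and gains little at mid-ages. At 18 and 60 both models are wider than the cell mean, although the 40-60 cell mean carries its own bias at its edges.

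Finally, Table 1's cells are enrolment cells, so age at entry is the natural reading. That is fair, but it does not place ages 30 and 40.

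**Conclusion.** The point holds as a modest one. The only concretely specified age comparison uses three bands that overlap at 30 and 40; the age-volume relationship and age normalisation have no stated form. Under a linear age effect and the assumptions above, banding costs about 9 to 18 points of power against a linear term and about 5 to 7 against a spline in 102 people, and one mean for ages 40 to 60 misstates its ends by 0.18 to 0.33 SD. Those sizes are illustrative. The overlap and the decade mismatch need no assumption.

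Three stronger readings are not supported. The sample size of 102 is not made wrong by the overlap. No effect on the primary ROC cut-offs is shown, because Section 6.2.3 does not use the bands. And no passage proposes reference limits of the mean-minus-multiple-of-SD kind, so no loss can be claimed for them.

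**What to change.** In Section 6, make the main healthy-control age analysis one regression of cord volume on continuous baseline age, sex and age-by-sex. Prespecify a three-knot restricted cubic spline, with knot positions and the criterion for non-linearity, to replace the linear term if that criterion is met. Take age- and sex-specific expected values with 95% confidence intervals from this model.

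Keep the bands and their SDs for recruitment and for the descriptive endpoint. Make them mutually exclusive (for example 18-29, 30-39, 40-60), fix them by age at baseline, and use them wherever the text now refers to decades.

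The cost is wording in the analysis section and new labels in Table 1; no extra participants or scans. The price in assumptions is a smooth age effect: bands do better for a step at 40, a linear term alone misses a peak, and estimates at 18 and 60 are less precise than cell means, most of all with the spline (men 0.89 and 1.02 SD against 0.57).

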During 2016 we have developed an in-house semiautomatic pipeline for measurement of cervical spinal cord volume that is a part of Scanview program. The segmentation is performed on T2-weighted images. In the first step, a marker is manually placed in a center of an intervertebral disc C3-4 (sagittal plane). Subsequently a cord straightening (manual rotation of the cord to achieve a perpendicular orientation of spinal cord to dorsal part of C3 vertebral body), that enable to reduce partial volume due to the cord orientation. After this centering and straightening, transformation matrix is saved and all subsequent steps are fully automatized. These steps include: 1. Sub-pixel division, 2. Reversing the contrast of T2-weighted images and smoothing by applying a set of median, Gaussian and edge-enhancing filters and 4. Cubic spline interpolation to find a curve that represents a border of a spinal cord with highest probability. Finally, a sum of mean areas of 21 1-mm slices is calculated (1 center slice fixed at center of a intervertebral disc C3-4 and 2 x 10 slices in cranial and caudal direction).

Using this new software we have assessed 1,036 MS patients during 2016 and 2017. The intra- and inter-rater variability of SC volume assessment was done by using the intraclass correlation coefficient (ICC) with a two-way mixed absolute agreement and single-measures design. The analysis confirmed very good consistency (> 98%) of the method. The preliminary

results showed a significant correlation between spinal cord volume and different clinical phenotypes.

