2.1. Study Rationale

To be able reliably evaluate spinal cord volume and its changes in MS patients we need to understand variability of these parameters in sex and age matched healthy controls. To date, no generally available data about these parameters in healthy controls are available. In addition, the result are scanner specific and using particular scanner we need to get these physiologic ranges particularly for the type of scanner where MS patients are evaluated.

The objective of this study is to investigate age and sex matched healthy controls by MRI to get the basic set of the data representing both cross sectional values and its longitudinal changes.

The present study will also investigate different strategies how to normalize the absolute spinal cord and brain volume data, what is a relationship between spinal cord volume and brain volume data and what is the best protocol to be used in a routine clinical practice

STUDY OBJECTIVES AND ENDPOINTS

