2.2.2. Secondary Objectives

The secondary objectives of this study are as follows:

- Test several normalization strategies and choose the best variable or set of variables to normalize spinal cord volume
- Determine inter-subject variability in spinal cord volume in healthy subjects
- Determine inter-subject variability in different whole and regional brain volumes in healthy controls

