3.2. Overall Study Duration and Follow-Up

The study period will be overall 4 years. During first 12 months we plan to enroll 102 HC. The enrollment period will take maximum 12 months. The study duration for a particular subject will be 3 years. During this period each participant will be examined by MRI at month 0, 12, 24, and 36.

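### A raw SD of per-person slopes would overstate the physiologic variability of cord atrophy, by an amount the documents do not fix; the plan should estimate the error-corrected spread

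*Combined protocol and SAP*

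**What the plan says.** The title in the Synopsis names the target: "Physiologic interindividual variability of volume and atrophy in central nervous system structures". Section 2.1 gives the reason: "To be able reliably evaluate spinal cord volume and its changes in MS patients we need to understand variability of these parameters", where the parameters are cord volume and its changes. The listed secondary objective in Section 2.2.2 is narrower and concerns volume only: "Determine inter-subject variability in spinal cord volume in healthy subjects".

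Individual change is defined once, under Statistical Methods in the Synopsis: "Annualised change of spinal cord volume will be calculated for each participant as the slope of a regression line fitted to all four timepoints". The sentence goes on "with the assumption of linear change over time for each participant and for all participant (in a decade-specific manner) together". So a pooled fit is also planned, but its form is not stated and no random effects are mentioned. Section 6 does not repeat the slope definition. It plans logistic regression and ROC analysis for cut-offs of change over three years (6.2.3). Continuous variables are summarised by mean, SD, median and range (6.2.2, 6.2.4).

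The schedule is in Section 3.2: "During this period each participant will be examined by MRI at month 0, 12, 24, and 36". The only reliability evidence is in the Introduction, an intraclass correlation for intra- and inter-rater variability: "The analysis confirmed very good consistency (> 98%) of the method". No scan-rescan error, between-person CV, healthy atrophy rate or slope SD is given anywhere.

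**The concern.** A least-squares slope through four scans carries the error of those scans. The SD of such slopes across people therefore mixes two things: how much healthy people truly differ in their rate of cord loss, and how imprecisely four scans measure that rate. The plan provides SD and range as its only summaries of spread and no step that separates the two. If the raw SD or range of slopes is published as the physiologic variability of atrophy, it is too wide as a statement about biology. Part of it belongs to the scanner, the segmentation software and the visit schedule.

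The reliability figure does not settle this. A high ICC means that error is small relative to differences in volume between people. Change within one person over three years is a much smaller signal, and the same error may be large relative to it. The Introduction itself lists field inhomogeneity and motion of the cord and cerebrospinal fluid as difficulties, and it does not say that the rater figure covers repeat scans.

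**Working it through.** **The plan's own figure.** Section 6.3.2 takes 10 per cell plus 2 for dropout, with a 1:2 male-to-female ratio over three age bands: 3 × (10 + 2) + 3 × (20 + 2) = 36 + 66 = 102. This reproduces. It is a rule of thumb and involves no assumption about slope spread or error.

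**What follows from the schedule alone.** Let σ be the within-person error SD per scan and τ the true SD of slopes.
- For t = 0, 1, 2, 3 years, Σ(t − mean)² = 5. The error SD of one slope is σ/√5 = 0.447σ.
- Observed slope variance = τ² + σ²/5. It exceeds τ² whenever σ > 0.
- Error is more than half of the slope variance only if τ < 0.447σ.
- If month 36 is missed and a slope is still fitted, Σ(t − mean)² = 2 and the error SD is 0.707σ. Section 6.2.1 analyses all available data and Section 6.3.2 expects dropout, so missed visits alone can change the spread.
- Each complete series leaves 4 − 2 = 2 residual degrees of freedom, 102 × 2 = 204 in all. The design can therefore estimate σ.

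**Volume.** At ICC 0.98, error is 2% of the variance of volume and inflates its SD by 1/√0.98 = 1.01. The listed volume objective is not affected in practice.

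**Change, under assumptions.** Take σ = √(1 − ICC) × CV, with CV the between-person SD as a percentage of mean volume. Only ICC > 98% comes from the documents. CV, τ and the use of a rater ICC for scan-to-scan error are assumptions.

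| ICC | CV (%) | σ (%) | σ/√5 (%/yr) | τ (%/yr) | Error share of slope variance | Observed SD / τ |
|---|---|---|---|---|---|---|
| 0.99 | 8 | 0.80 | 0.36 | 0.5 | 34% | 1.23 |
| 0.98 | 10 | 1.41 | 0.63 | 0.3 | 82% | 2.33 |
| 0.98 | 10 | 1.41 | 0.63 | 0.2 | 91% | 3.32 |
| 0.98 | 6 | 0.85 | 0.38 | 1.0 | 13% | 1.07 |
| 0.995 | 6 | 0.42 | 0.19 | 0.5 | 13% | 1.07 |
| 0.995 | 6 | 0.42 | 0.19 | 1.0 | 3% | 1.02 |

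In the second row the observed SD is √(0.3² + 0.63²) = 0.70 instead of 0.30. Without month 36 it would be √(0.3² + 1.41²/2) = 1.04. With σ set directly between 0.5% and 3%, and τ between 0.2 and 1.0, the error share runs from 5% to 98%.

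**Can the error be removed?** In 3,000 simulated cohorts per setting, the slope variance minus pooled residual variance/5 was computed, with σ = 1.4%.

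| n | τ (%/yr) | Mean raw SD | Corrected SD (root of mean variance) | Central 95% range of corrected SD | Estimate ≤ 0 |
|---|---|---|---|---|---|
| 102 | 0.3 | 0.69 | 0.30 | 0 to 0.50 | 13% |
| 102 | 0.5 | 0.80 | 0.50 | 0.25 to 0.67 | 0% |
| 12 | 0.5 | 0.79 | 0.51 | 0 to 0.96 | 19% |

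The correction removes the bias. It is usable for the whole cohort and too imprecise in a cell of 12.

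**The case against.** The strongest reply has four parts.

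1. *The documents never say that a raw slope SD will be called physiologic.* That is so. It is inferred from the title, the rationale and the general summary-statistics text. But the plan offers no other summary of spread for change, and the pooled fit has no stated form.

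2. *The listed variability objective and the comparison of variability in Section 6.2.4 concern volume.* This stands. Section 6.2.4 covers the secondary endpoints, which describe volumes and normalisation. A reader might infer that a listed objective is overstated or a planned group comparison invalid; the documents do not support either.

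3. *The size rests on chosen inputs.* This also stands. A reader might infer that the slope spread is largely noise. That needs a scan-rescan SD and a true slope SD, and the documents give neither; plausible inputs fall on both sides of one half. The rater ICC may understate scan-to-scan error, which would raise the share, but this too cannot be quantified.

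4. *For the cut-offs of change, the observed spread is the right reference.* This is correct. A patient's slope carries the same kind of error, and Section 2.1 wants scanner-specific ranges. In the example with a true SD of 0.30 and an observed SD of 0.70, a lower 2.5% limit built from 0.30 lies 1.96 × 0.30 = 0.59 below the mean. That is 0.59/0.70 = 0.84 observed SDs, so under normality about 20% of healthy people would fall below it. The primary endpoint is therefore not at fault here.

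**Conclusion.** The point holds as a matter of estimation. The title and rationale ask for the physiologic variability of atrophy, the plan supplies only raw slopes and their SD or range, and that spread contains σ²/5 on top of the true variance with no correction. The direction of the bias follows from the schedule and needs no outside figure.

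The size is open. With ICC 0.98-0.99, CV 8-10% and true slope SD 0.2-0.5% per year, the error share is 34-91% and the SD is inflated 1.2 to 3.3 times. With a CV of 6% and either a true slope SD of 1.0 (at ICC 0.98) or an ICC of 0.995 (at true SD 0.5), the share falls to about 13%, and with both to about 3%. That the plan cannot tell which case applies, although its own data could, is the reason to change it.

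**What to change.** Add a paragraph to Section 6:

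- For the whole healthy cohort, estimate the between-person SD of annual change from a mixed model with random intercept and random slope on the four scans, with a confidence interval. Alternatively, use slope variance minus pooled residual variance/5, with the divisor adjusted for missed visits.
- Report the within-person residual SD beside it as an indication of measurement error, noting that it also absorbs non-linear change. Report scan-rescan error if it is available.
- Label any raw slope SD or range as observed.
- State the form of the pooled decade-specific fit so that it agrees with this model.
- Keep the observed slope distribution for the HC-versus-MS cut-offs of change in Section 6.2.3, and say that the corrected SD is not to be used for them.
- If variability of change is compared between groups, compare the error-corrected slope SDs and show the residual SDs beside them. The residual SD should not itself be the comparison, since it measures mainly noise.

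The cost is SAP wording and one model on data already planned. The drawback is precision: for a true SD of 0.3% per year and σ = 1.4%, estimates from 102 people range from about 0 to 0.50. A corrected SD should not be promised for the age-sex cells of 12 to 22. Only 12 was simulated, but 22 lies far nearer to 12 than to 102.
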